#### 4.7.3 Medical Research Council sum score (MRC sum score)

The Medical Research Council sum score (MRC sum score) used for the efficacy endpoints will be assessed for all subjects as per the schedule of assessments. It is a sum score of power in six muscle groups on each side (summing all the obtained scores of each muscle groups on each side). The sum of these scores ranges from 0 (total paralysis) to 60 (normal power). The individual MRC grades are defined as:

0=No visible contraction

1=Visible contraction without movement of the limb

2=Movement of the limb but not against gravity

3=Movement against gravity (almost full range)

4=Movement against gravity and resistance

5=Normal

Summary statistics will be presented in tables for the actual values and absolute change from baseline for MRC sum score by time point. MRC sum score will be calculated only if all 12 scores of each muscle groups on each side have data, otherwise this will be missing.

In addition, representing proximal and distal muscles outcomes, summary statistics (both actual values and absolute change from baseline) will be presented for the following four subgroups of the MRC score (sub-scores), calculated as an average of the included items, by time point:

- abduction of arm + flexion of forearm for both sides
- extension of the wrist for both sides
- hip flexion + extension of knee at both sides
- dorsal flexion of the foot for both sides

Sub-scores including one muscle group will be calculated if both sides have scores, sub-scores including two muscle groups will be calculated if both muscle groups have scores from at least one side. This does mean that the MRC sum score may be missing even though some sub-scores are calculated (due to available data for the scores in particular muscle groups).

Individual subject plots will be created showing both MRC sub-scores and GBS DS over time up to Day 92 (collected as part of Visit 8). The graph will show time since imlifidase administration on x-axis, MRC sub-scores over time will be represented as a line, GBS DS as a bar coloured according to latest GBS DS. Additional events of interest will be included on the plot: onset date of worsening of GBS (captured as AE: any AE with reporter term stating 'FACIAL PARALYSIS', or AE coded preferred term of 'Neuropathy peripheral' or 'Respiratory failure' with corresponding reported term suggesting worsening/deterioration of GBS), start and stop dates for ICU admission(s).

#### 4.7.4 Ventilator support and days in hospital and days in an ICU

The number and percentage of subjects requiring mechanical ventilation support (GBS DS 5) will be presented by time point.

In addition, summary statistics will be presented in three separate tables for the number of days on mechanical ventilation and number of days in hospital and in an ICU. The number of days in an ICU is a subset of number of days in hospital.

The total number of days on mechanical ventilation and total number of days in hospital and in an ICU will be calculated for each subject considering the following formula:

Total number of days on mechanical ventilator = Sum of [(End date of mechanical ventilation – Start date of mechanical ventilation) + 1]

Total number of days in hospital = Sum of [(End date in hospital – Start date in hospital) + 1]

Total number of days in an ICU = Sum of [(End date in an ICU – Start date in an ICU) + 1],

including each period the subject was on mechanical ventilator in hospital and in an ICU between administration of IMP to Day 180. As periods can overlap (new period starting at the same date that previous period ended) it will be ensured that no day is counted twice.

Also, the number and percentage of subjects that were at ICU or on mechanical ventilator at time of imlifidase administration will be presented in a separate table on the FAS, part of the baseline characteristics section.

Details about the mechanical ventilation support, hospital admission and days in an ICU will be presented in separate listings.

## 4.7.5 EurQol EQ-5D-5L Health Questionnaire

Quality of Life is used for assessment of efficacy and is measured by EuroQol EQ-5D Health Questionnaire. The EQ-5D-5L consists of 5 individual items (mobility, self-care, usual activities, pain/discomfort, anxiety/depression) and an EQ Visual Analogue scale (EQ VAS) and EQ-5D-5L is designed for self-completion by respondents. EQ-5D-5L will be completed by the participating subjects as per the schedule of assessments.

Summary statistics will be presented in a table for the VAS score by time point. Also, all individual items will be summarized using frequency counts and associated percentages for all time points in a separate table.

## 4.8 Safety

Safety data will be presented by descriptive statistics in tables and in listings for each subject. Safety parameters will be evaluated for the safety analysis data set.

### 4.8.1 Adverse events

According to the protocol, an AE is defined as the development of an undesirable medical condition or the deterioration of a pre-existing medical condition following or during exposure to a pharmaceutical product, whether or not considered causally related to the product. Relationship to the study drug will be deemed as not related, unlikely, possible or probable. An undesirable medical condition can be symptoms (e.g., nausea and chest pain), signs (e.g., tachycardia and enlarged liver) or the abnormal results of an investigation (e.g., laboratory findings and electrocardiograms).

A pre-treatment adverse event is any untoward medical occurrence arising or observed between signing of informed consent and administration of the IMP.

A treatment emergent adverse event (TEAE) is any AE occurring after the start of administration of the IMP and within the time of residual drug effect, or a pre-treatment AE or pre-existing medical condition that worsens in intensity after start of administration of the IMP and within the time of residual drug effect.

The time of residual drug effect is the estimated period after the administration of the IMP, where the effect of the product is still considered to be present based on pharmacokinetic, pharmacodynamic or other substance characteristics. The residual drug effect is generally accepted to be 5 times the terminal half-life. The terminal half-life of imlifidase is expected to be within the range of approx. 100 hours, i.e. in this study the residual drug effect is likely to be well within the Day 29 assessments, but since this is the first administration of imlifidase to GBS subjects, all AEs occurring up to Day 29 are regarded as treatment emergent.

A Serious Adverse Event (SAE) is defined as an AE which fulfills any of the following:

- Results in death
- Is immediately life-threatening
- Requires in-patient hospitalization or prolongation of existing hospitalization

- Results in persistent or significant disability or incapacity
- Is a congenital abnormality or birth defect
- Is an important medical event that may jeopardize the patient or may require medical intervention to prevent one of the outcomes listed above. Examples of such events include allergic bronchospasm requiring intensive treatment in an emergency room or at home, blood dyscrasias or convulsions that do not result in inpatient hospitalization, or the development of drug dependency or drug abuse.

For surgical or diagnostic procedures, the condition/illness leading to such a procedure is considered as the AE, but not the procedure itself.

The following events will be assessed as adverse events of special interest (AESI):

- Infusion-related reactions that occurs within 48 hours of imlifidase treatment
- All AEs resulting in interruption (pause and/or discontinuation) of imlifidase dose (exempted are all interruptions due to problems with e.g., infusion line or pump)
- Severe or serious infections within 30 days after imlifidase administration

AEs will be coded according to Medical Dictionary for Regulatory Activities (MedDRA) version 21.1.

Summary tables will be presented for all AEs and TEAEs, respectively. For each of the AE categories below, the number of subjects reporting an AE, the percentage of subjects with an AE and the number of events reported:

- All AEs
- TEAEs
- All non-TEAEs divided in pre- and post-TEAE
- AEs having CTCAE grade  $\geq 3$
- TEAEs having CTCAE grade  $\geq 3$
- All non-TEAE having CTCAE grade  $\geq 3$  divided in pre- and post-TEAE
- SAEs
- Serious TEAEs
- Adverse Drug Reactions (ADR) defined as TEAEs related to study treatment (i.e., Possibly or Probably Related AEs)
- AEs leading to withdrawal
- TEAEs leading to withdrawal
- AEs leading to death
- AEs of special interest (AESI).

Summary tables will be prepared for the incidence of all AEs and TEAEs, respectively, by MedDRA System Organ Class (SOC) and Preferred Term (PT), presenting number of subjects reporting an AE, the percentage of subjects (%) with an AE and the number of events reported. Summary tables will be prepared for:

- All AEs by SOC and PT
- All TEAEs by SOC and PT
- All pre-TEAEs by SOC and PT

- All post-TEAEs by SOC and PT
- AEs by SOC, PT and causality (related/not-related)
- TEAEs by SOC, PT and causality (related/not-related)
- Pre-TEAE by SOC, PT and causality (related/not-related)
- Post-TEAE by SOC, PT and causality (related/not-related)
- AEs by SOC, PT and intensity
- TEAEs by SOC, PT and intensity
- Pre-TEAE by SOC, PT and intensity
- Post-TEAE by SOC, PT and intensity
- TEADRs by SOC and PT
- Post-Treatment emergent ADRs by SOC and PT
- TEADRs by SOC and PT and intensity
- Post-Treatment emergent ADR by SOC, PT and intensity

Missing values will be treated as missing except for causality, intensity, seriousness and outcome of an AE, in which case, a “worst case” approach will be taken. Thus, if causality is missing, the AE will be regarded as related to the IMP, if intensity of the AE is missing, it will be taken to be severe, if seriousness is missing, the AE will be considered as an SAE and if the outcome is missing and no date of outcome is present, the outcome is regarded as “not yet recovered”.

Listing will be provided for:

- All AEs
- TEAEs
- Pre-treatment AEs
- Post-treatment emergent AEs
- AEs having CTCAE grade  $\geq 3$  divided in Pre-TEAE, TEAE and Post-TEAEs
- SAEs divided in Pre-TEAE, TEAE and Post-TEAEs
- Adverse Drug Reactions (ADR) divided in TEAE and Post-TEAEs
- AEs leading to withdrawal divided in Pre-TEAE, TEAE and Post-TEAEs
- Deaths (ie AEs leading to death) divided in Pre-TEAE, TEAE and Post-TEAEs
- Adverse events of special interest (AESI) divided in TEAE and Post-TEAEs

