#### 9.2.1.1 Causality Assessment

For each reported AE the investigator will make an assessment of the relationship of the event to study procedures and/or IMP using the following criteria.

- **Unrelated:** applicable to an AE that occurs when the subject was not exposed to study treatment or another cause is obvious.
- **Unlikely to be related:** applicable to an AE that meets the following criteria
  - Does not follow a reasonable temporal sequence from study drug dosing
  - May readily have been produced by the subject's clinical state, environmental, or toxic factors, or other therapy administered to the subject
- **Possibly related:** applicable to AEs where connection with dosing of study drug appears unlikely but cannot be ruled out. Applicable to AEs where
  - It follows a reasonable temporal sequence dosing with study drug
  - It follows a known pattern of response to study drug dosing (based on previous studies)

- **Probably related:** applicable to AEs that are considered, with a high degree of certainty, to be related to the study drug. Applicable to AEs where
  - It follows a reasonable temporal sequence study drug dosing
  - It cannot be reasonably explained by the known characteristics of the subject's clinical state, environmental or toxic factors, or other modes of therapy
  - It follows a known pattern of response to study drug dosing (based on previous data).
- For SAEs causal relationship will also be assessed for any study procedure.

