### **12.3.1 Analysis of Adverse Events**

AEs will be coded according to the latest version of the MedDRA. All data will be listed by subject. Only treatment emergent AEs will be presented in summary tables. Separate data listing will be provided for AEs that are defined as pre-treatment or post-treatment emergent.

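### The SAP's worst-case rule for missing causality is not limited to events after dosing, so a pre-treatment AE with missing causality would be tabulated as related to imlifidase

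*SAP*

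**What the plan says.** The rule in SAP section 4.8.1 opens with "Missing values will be treated as missing except for causality, intensity, seriousness and outcome of an AE". For the first two of these fields it then says "if causality is missing, the AE will be regarded as related to the IMP, if intensity of the AE is missing, it will be taken" as severe. Nothing in the paragraph confines it to treatment-emergent events.

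The same section lists the AE summary tables. They include all AEs by causality and, separately, "Pre-TEAE by SOC, PT and causality (related/not-related)". There are matching tables by intensity, and the overview table has a pre-treatment row for CTCAE grade 3 or higher.

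The protocol is narrower. Section 12.3.1 says "Only treatment emergent AEs will be presented in summary tables", and the same worst-case rule appears in section 12.3.2.1, whose subject is the incidence of treatment-emergent AEs. On causality, protocol section 9.2.1.1 defines its Unrelated category as "applicable to an AE that occurs when the subject was not exposed to study treatment or another cause is obvious".

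SAP section 6, which lists departures from the protocol analysis, mentions neither the added pre-treatment tables nor the wider reach of the rule.

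**The concern.** A worst-case imputation is defensible when the unfavourable value is a possible one. For an AE that starts after imlifidase, related is possible, and assuming it is cautious. For an AE that starts between consent and dosing, it is not possible: the subject has not yet received the drug. The rule then enters a value that the protocol's own causality categories rule out.

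At stake is the accuracy of the related column in two safety tables, and their agreement with the ADR outputs. The same event could appear as related to imlifidase in the all-AE causality table and in no ADR table or listing.

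**Working it through.** The plan states no figure for this rule, so there is nothing to reproduce. The check follows one record through the definitions and then bounds the effect.

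**Causality**

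1. Take an AE that starts after consent and before imlifidase, with the causality field blank. SAP 4.8.1 classes it as a pre-treatment AE.
2. The missing-value rule covers any AE, so causality becomes related to the IMP.
3. The record enters the related column of the pre-TEAE causality table and of the all-AE causality table.
4. Protocol 9.2.1.1 puts an AE in an unexposed subject under Unrelated. Steps 2 and 4 contradict each other.
5. SAP 4.8.1 defines ADRs as related TEAEs. Its ADR tables and listing cover treatment-emergent and post-treatment events only, so this record reaches none of them.

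**Size**

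- About 30 subjects are planned (SAP 2.2). One affected subject moves a subject incidence by at most 1/30 = 0.033, or 3.3 percentage points. If that subject is already counted in the cell, the incidence does not move and only the event count rises.
- Protocol 4.1 places dosing within 24 hours of consent, so the pre-treatment window is short.

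**Intensity (secondary and conditional)**

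The TEAE definition has two limbs. The first covers any AE occurring after the start of imlifidase and within the residual-effect period. The second covers an earlier AE, or a "pre-existing medical condition that worsens in intensity after start of administration of the IMP". The second limb compares grades before and after dosing. Suppose, as an assumption, that a missing pre-dose grade were replaced by severe for that comparison. SAP 1.1.2.2 equates severe with CTCAE grade 3 or higher and fixes no single grade, so two values are shown.

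With grades 1 to 5, pre-dose grade g from 1 to 4 and post-dose grade h > g, the possible true worsenings number 4 + 3 + 2 + 1 = 10. A worsening is masked when h does not exceed the imputed grade.

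| Imputed pre-dose grade | Masked pairs (g to h) | Masked | Still flagged |
|---|---|---|---|
| 3 | 1 to 2, 1 to 3, 2 to 3 | 3 of 10 | 7 |
| 4 | the three above, plus 1 to 4, 2 to 4, 3 to 4 | 6 of 10 | 4 |

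The error can also run the other way: with grade 3 imputed, a true grade 4 event that stays at grade 4 would be flagged as worsened. These are counts of possible grade pairs, not event frequencies.

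**The case against.** The strongest defence of the causality rule is that it hardly ever operates. The investigator must assess causality for every AE, the protocol supplies a category for unexposed subjects, the window is about a day, and the ADR outputs are untouched. An event wrongly called related in a table labelled pre-treatment would mislead few readers. All of this stands and limits the size. It does not remove the contradiction, and the all-AE causality table carries no pre-treatment label to warn the reader.

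A reader might go further and infer that the intensity rule removes real treatment-emergent worsening from the TEAE tables. The documents do not support that as a finding:

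- The only imputation that the SAP ties to TEAE flagging is that of dates (section 4.1.3). The intensity rule follows the list of summary tables and can be read as a tabulation rule.
- Protocol 9.2.1 lists severity as one variable per AE. It does not describe paired pre-dose and post-dose grades within a record.
- A worsening entered as a new AE with a post-dose start is a TEAE under the first limb, whatever the earlier grade.
- Conditions held only in medical history are not AE records, so the rule for missing AE fields does not reach them.
- The number of masked pairs depends on which grade severe is taken to mean.

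What remains is that the SAP does not say whether imputed intensity may serve as the pre-dose reference, and a programmer would have to choose.

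**Conclusion.** The causality point holds on the text alone: a rule carried over from the treatment-emergent setting gives a wrong value when applied to pre-treatment AEs. It affects the pre-TEAE and all-AE causality tables and leaves the ADR outputs alone. The impact is minor: few events, and at most 3.3 points per affected subject in any cell, taking 30 subjects as the denominator.

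The intensity point is a request for clarification. Masking needs three things together: an imputed grade used for TEAE flagging, a missing pre-dose grade beside a recorded later one, and a worsening not entered as a new AE. The documents establish none of these.

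**What to change.** In SAP 4.8.1:

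1. Limit the worst-case causality imputation to AEs with onset at or after the start of imlifidase, and class pre-treatment AEs with missing causality as not related to the IMP. Add that a pre-treatment AE counted as a TEAE because it worsened after dosing is handled as a TEAE and keeps the worst-case rule, so that no possible ADR is lost.
2. State that imputed intensity is used for tabulation only and not as the pre-dose reference for TEAE flagging. Keep the worst-case intensity rule for the intensity tables. Dropping it for pre-treatment AEs would leave the pre-TEAE intensity table and the pre-treatment row for grade 3 or higher without a rule.

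If AE records can carry grades from both before and after dosing, the SAP should also say how worsening is judged when the earlier grade is missing. Any choice is a convention. Assuming the lowest grade, for example, would flag an unchanged grade 2 or 3 event as treatment-emergent.

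The cost is two or three sentences and one derivation condition, with no new data. The change should also be listed in SAP section 6.

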## 4.8.2 Other safety endpoints

### 4.8.2.1 Anti-imlifidase antibodies (ADA)

Presence of anti-imlifidase antibodies (ADA) will be assessed. The long-term effect of treatment will be evaluated by presenting summary statistics for each time point, for antibodies anti-imlifidase IgG (ADA) values. A listing will also present the ADA results collected over time by time point.

Antibodies anti-imlifidase IgG (ADA) values below lower limit of quantification (LLOQ) will be imputed using the limit itself.

Boxplots corresponding to the ADA results collected over time will be presented by time point. Also, individual plots will be presented for each subject to show the ADA results over time point in two separate set of plots: one up to Day 29 (collected part of Visit 6) and one up to Day 180 (collected part of Visit 9).

#### 4.8.2.2 Vital signs

Vital signs will be presented by visit (i.e., time point) for each parameter and summarised, including absolute change from baseline. Shift tables will be presented from baseline to all planned time points until end of residual drug effect, i.e. Day 29. Any changes from normal/low to high or from normal/high to low during these periods will be counted as a shift and will be summarised. The results will be flagged as Low (L)/High (H) as per the criteria defined in [Appendix 3](#).

In addition, separate listings containing vital signs data will be presented by subject.

The vital signs assessment part of visit 3, 7 and 9 has only been collected up to protocol version 7.0 (inclusive). Results from these visits will only be presented in the listing.

#### 4.8.2.3 Clinical Chemistry, Haematology and Urinalysis

Laboratory tests will be summarised and presented in tables similarly as the vital signs parameters. In addition, shift tables for normal, abnormal and not clinically significant, abnormal and clinically significant results will be presented for all clinical chemistry and haematology laboratory parameters from baseline to all planned time points until end of residual drug effect, i.e. Day 29. Similar shift tables will be presented also for urinalysis parameters from baseline to all planned time points until end of residual drug effect, i.e. Day 29. Listings containing laboratory test data will be presented by subject. Abnormal clinically significant values will be flagged in listings.

The safety laboratory assessment part of visit 7 and 9 has only been collected up to protocol version 7.0 (inclusive). Results from these visits will only be presented in the listings.

#### 4.8.2.4 Electrocardiography (ECG)

ECGs will be categorised as “normal”, “abnormal, not clinically significant”, or “abnormal, clinically significant” (as judged by the Investigator) and listed by subject.

#### 4.8.2.5 Physical examination

A complete physical examination will be performed at screening and Day 180 (visit 9). The physical examination will be listed by subject.

### 4.9 Other endpoints

#### 4.9.1 Anti-ganglioside antibodies

Biomarker assessment (analysis of anti-ganglioside antibodies and neurofilament light chain levels) will be evaluated as an exploratory endpoint.

Pre-dose samples will be screened for anti-ganglioside antibodies and presented in a table as positive or negative. The anti-ganglioside antibodies data will be listed by subject.

Neurofilament light chain levels will be summarized in a table and presented in a listing by subject. In addition, neurofilament light chain levels will be presented both as mean plot and individual subject plots to show the change over time.

Moreover, a separate plot will show anti-ganglioside antibodies titers per subject over time up to Day 92 (collected as part of Visit 8) together with the swimmer plot of the GBS disability scores and the subgroup MRC scores on FAS.

